# 8. STUDY CALENDAR (28 day Cycle) Table 16: Study Calendar

	Screening		Treatment Period							End of Treatment Visit 	Follow- Up 		
		Cycle 1					Cycle 2			From Cycle 3			
Day of cycle	-21 to -1	1 	5	26	28	1 	26	28	1 	26	28	1	
Assessments 													
Informed Consent	Х												
Demographics with body height (cm)	Х												
Medical History	Х												
Disease history (including number of prior therapy regimens for ALL)	Х												
Inclusion/Exclusion	X												
ID Panel	X 												
Pregnancy Test	X 	X 				X 			X 			X 	
Vital Signs and body measurements													
ECOG Performance Status	X	Χ				X			Χ			X	X
Weight (kg)	Х	Χ				X			Χ			X	X
Physical Exam	Х	Χ		X 		Χ	X 3		Χ	X 		X	X
Eye examination (see Section 8.4)	X			Х			X			Х		X	X
Body Temperature	Х	Х				X			Χ			X	X
Respiratory rate	Х	Х				X			Χ			X	Х
Cardiac assessments													
Blood Pressure	Х	Х		Х		X	Х		Χ	Х		X	
12-Lead EKG	X 	Х	Х			Χ			Χ			X	
ECHO or MUGA	X 	X 				X			Χ			X	
Standard Laboratory Procedures													
Biochemistry 	Х	Χ	Х	Х		X	Х		Χ	Х			
Hematology 	Х	Х	Χ	Х		X	Х		Χ	Х			
Coagulation 	Х	Х	Х	Х		X	Х		Χ	Х			
Disease Assessment 	Х	X 		Х		X 	Х		X 	Х			X 
Pharmacokinetic profile 		Х	Х										
Biomarker Assessments 		Х	Х	Х			Х			Х		Х	
Lumbar puncture & CSF sampling 	Х			Х			Χ			Х			
Concomitant Medications	Х	Х	Х	Х		Χ	Х		X 	X 			
Adverse Events	Х	Х	Х	Х		Χ	Χ		Χ	Х		Х	Х
Survival Status				_									Х

Protocol 2021-0547 4/25/2024

- 1. Assessments scheduled on days of dosing should be done prior to administration of study drug(s), unless otherwise specified.
- 2. Screening assessments can be used as day 1 assessments of cycle 1 if done within the previous 72 hrs.
- 3. End of previous cycle assessments (Day 26) can be used as day 1 assessments if done within Day 26-29. If subsequent cycle is delayed, hematology, chemistry, and coagulation labs and physical exam assessments should be repeated on Day 1 of cycle.
- 4. For women of childbearing potential only. Serum pregnancy test must be performed within 24-48 hours before first study treatment. During the on-treatment period and at the EoT visit, urine pregnancy testing should be done as indicated in the table or whenever a pregnancy is suspected. Pregnancy and suspected pregnancy occurring while the patient is on study drug treatment or within 90 days after the last dose of CB-103 should be reported to the supporting company (Cellestia AG).
- 5. Screening assessments can be used as day 1 assessments if done within the previous 14 days.
- 6. EKG and LVEF assessment by ECHO or MUGA should be done within 14 days before first study treatment: these assessments may be repeated at the Investigator's discretion in case of signs or symptoms of cardiotoxicity. See Sections 8.7.1 and 8.7.2.
- 7. Tests will be performed at least 2 times weekly during the first treatment cycle and at least 1 time weekly during each successive treatment cycle. Outside labs will be permitted and the PI/treating physician will review the labs for clinical significance, and sign/date the results. If patients present treatment-related toxicities, monitor blood counts and chemistries as clinically indicated. This assessment does not need to be repeated at Cycle 1, Day 1 if it was performed at screening within 48 hours prior to start of study treatment.
- 8. Laboratory tests to be performed locally, within 48 hours before study visit (Day 1 of each cycle, including Cycle 1, Day 1) include albumin, alkaline phosphatase, alanine aminotransferase (ALT), aspartate aminotransferase (AST), lactate dehydrogenase (LDH), carbon dioxide (CO2), uric acid, calcium, chloride, glucose, phosphorus, potassium, sodium, magnesium, total bilirubin, direct bilirubin (if total bilirubin is elevated above the upper limit normal), total protein, blood urea nitrogen (BUN) and creatinine.
- 9. CBC (WBC with differential, unless WBC <0.5 x109/L in which case differential not needed, Hemoglobin, and Platelet count).
- 10. Prothrombin time (PTT), activated partial thromboplastin time (aPTT), and fibrinogen. This assessment does not need to be repeated at Day 1 of cycles if it was performed within 3 days prior.
- 11. Disease assessment:
  - Bone marrow samples (aspirate and/or biopsy), cytogenetics, and flow cytometry: screening assessment can be used as day
    1 assessment of the induction cycle if done within the previous 3 weeks; end of previous cycle assessment can be used as day
    1 assessment of the next cycle if done in +/- 3 days.
  - At the baseline assessment, bone marrow biopsy and/or aspirate is within 21 days and no less than 1 day before the first drug
    dose.
  - Patients are assessed for disease response by bone marrow biopsy and/or aspirate on day 28 (±3 days) induction and subsequent cycles. If the blasts in bone marrow are <5% but marrow is hypocellular (cellularity ≤15%) on day 26, then a repeat bone marrow biopsy and/or aspirate is obtained 1 week later to assess response; if no clear definition of response to therapy may be determined, repeated bone marrow biopsy and/or aspirate will be obtained as clinically indicated.
  - For patients with extramedullary disease a PET-CT will be performed at baseline and if positive, also at C1D26, and Day 26 of all subsequent cycles (±3 days). Assessments should be performed as close as possible to the 1st drug administration and if feasible, a wider time window is allowed only at baseline, not later than 14 days prior to the 1st drug administration.
- 12. PK time sampling: blood sampling will be collected as per the schedule and time window indicated below:
  - C1D1: pre-dose, 2-, 6-hour post-morning dose, 2- hour post evening dose (± 5 minutes)
  - C1D5: pre-dose, 2-, 6-hour post-morning dose, 2- hour post evening dose (± 5 minutes)
  - PK Samples will be analyzed by a designated laboratory under Cellestia's responsibility.
- 13. Biomarker assessments: Serial blood and bone marrow samples will be obtained to measure gene and protein expression levels of relevant pathways (e.g. NOTCH, BCL2) as well as for longitudinal monitoring of tumor evolution by NGS if leftover sample is available. Baseline, at time of completion of induction (+/- 3 days), and reinduction cycles ± 3 days, and at time of progression. Additional blood samples will be collected on C1D5 and on Day 26 of all cycles for PD analysis by a designated laboratory under Cellestia's responsibility.
- 14. Lumbar puncture (T-ALL/T-LBL) for prophylactic intrathecal therapy: if prophylactic intrathecal therapy is foreseen by the treating physician, a lumbar puncture may be performed up to 3 days before the first dose of CB-103, and may be repeated at the discretion of the treating physician at the end of the first cycle and at the end of any subsequent cycles on or around day 28. If clinically feasible, one additional sample will be collected to determine the exposure of CB-103 in the CSF (this measurement will be done by a designated laboratory under Cellestia's responsibility).
- 15. For patients with PR or stable disease (SD) after the induction cycle(s) who may receive add-on selective therapy chosen by the investigator on the basis of the ongoing biomarker expression of the disease while continuing the treatment with the combination of CB-103 and venetoclax, the add-on therapy will be reported in details on the CRF.
- 16. EoT visit is to be done 5 days after the last dose of any study treatment, unless the patient starts any subsequent antitumor therapy (in which case the EoT visit should be performed before the start of the new therapy, whenever possible).
- 17 First follow-up visit will be 26 days after EoT (± 5 days), and every three months (± 14 days) thereafter, until EoS (i.e., death, patient's refusal, lost to follow-up) or study termination, whichever occurs first. Survival status and information on posterior antitumor therapies will be collected, telephone contact being acceptable.
- 18. If patient discontinued treatment without progression, tumor assessment will be done until progression or start of new antitumor treatment.
- 19. In case of relevant related toxicities (i.e., Grade>1), every 4 weeks until resolution or stabilization: information collected by telephone contact is acceptable.
- 20. Hepatitis B, C infection, and HIV will be obtained within 21 days of start of treatment.

Protocol 2021-0547 4/25/2024

#### 8.10 Outside Physician Participation During Treatment

- 1. MDACC Physician communications with the outside physician is required prior to the patient returning to the local physician. This will be documented in the patient record.
- 2. A letter to the local physician outlining the patient's participation in a clinical trial will request a local physician agreement to supervise the patient's care.
- 3. Protocol required evaluations outside MDACC will be documented by telephone, fax or email. The PI/treating physician must review the labs, determine clinical significance and sign and date the report.
- 4. A copy of the informed consent, treatment schema, and evaluation during treatment will be provided to the local physician.
- 5. Documentation to be provided by the local physician will include progress notes, reports of protocol required laboratory and diagnostic studies, and documentation of any hospitalizations.
- 6. The home physician will be requested to report to the MDACC physician investigator all life-threatening events within 24 hours of documented occurrence.
- 8. Changes in drug dose and/or schedule must be discussed with and approved by the MDACC physician investigator or their representative prior to initiation and will be documented in the patient record.

Page | 37 04/25/2024

#### 9. RESPONSE DEFINITIONS

Because morphologic examination of the bone marrow during periods of hematopoietic recovery after intensive chemotherapy may be unreliable, a response will be based on blast percentage by flow cytometry. Flow cytometric assessment of response (MRD) should be performed at MDACC. Blast percentages determined by morphology can be used in cases where the sample submitted for flow cytometry evaluation is limited or hemodiluted. Patients will be considered evaluable for response if they have been administered greater than 50% of the dose of CB-103. Patients will be evaluable for safety if they have been administered 1 dose of CB-103.

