#### 12. STATISTICAL CONSIDERATIONS

This is a phase II open-label single arm and single institution clinical trial to evaluate the efficacy and safety of CB-103 in combination with venetoclax in adolescent and adult patients with T-ALL/T-LL in first or second bone marrow recurrence refractory to initial induction therapy or refractory to at least one reinduction attempt. Up to 30 patients may be enrolled, without regard to Notch status; we anticipate that approximately 50% of these patients will be Notch positive. The primary efficacy endpoint of the study is overall response rate (ORR, including CR,CRi and PR rate) after the first two induction cycles, and the primary toxicity endpoint is the rate of toxic events, defined as a grade ≥3 non-haemtological AEs that are possibly or probably related to the study drugs (see Adverse Events (SAE) definition in section 9.2.2.1.) occurring during the 28 days of induction cycle.

We simultaneously monitor efficacy and toxicity using the Bayesian optimal phase 2 (BOP2) design [32]. Specifically, let n denote the interim sample size, and N denote the maximum sample size. Let  $Y_{eff}$  and  $Y_{tox}$  denote the binary efficacy and toxicity endpoints, with  $Y_{eff} = 1$  and  $Y_{tox} = 1$  indicating that patients experience efficacy and toxicity, respectively. We assume that the joint distribution of  $(Y_{eff}, Y_{tox})$  follows a multinomial distribution with four elementary outcomes:  $(Y_{eff}, Y_{tox}) = (1, 1), (1, 0), (0, 1)$  and (0, 0). Let  $\mathbf{p} = (P_{11}, P_{10}, P_{01}, P_{00})$  denote the probabilities of observing the four outcomes, and let  $P_{eff} = Pr(Y_{eff} = 1), P_{tox} = Pr(Y_{tox} = 1)$  and  $P_{efftox} = Pr(Y_{eff} = 1, Y_{tox} = 1)$ . When efficacy and toxicity endpoints are monitored separately, the joint distribution reduced to marginal distribution of efficacy and marginal distribution of toxicity, respectively.

The treatment is deemed unacceptable if  $p_{eff} \le 0.15$  or  $p_{tox} > 0.20$ . Thus, we will stop enrolling patients and claim that the treatment is unacceptable if

$$Pr(p_{eff} > 0.15|data) < \lambda \left(\frac{n}{N}\right)^{\alpha}$$

or

$$Pr(p_{tox} \le 0.20|data) < \lambda \left(\frac{n}{N}\right)^{\alpha/3},$$

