where  $\lambda$ =0.57 and  $\alpha$ =0.86 are design parameters optimized to maximize the study power, i.e., probability of correctly concluding an efficacious and safe **treatment as acceptable** when  $p_{eff}=0.3$ ,  $p_{tox}=0.10$  and  $p_{efftox}=0.05$ , while controlling that the probability of incorrectly claiming an inefficacious and toxic treatment, i.e., type I error, with  $p_{eff}=0.15$ ,  $p_{tox}=0.20$  and  $p_{efftox}=0.05$ , to 8.3%. Note that in the safety stopping rule, the original publication of the design used the probability cutoff  $\lambda(n/N)^{\alpha}$ , here the attenuation factor 3 is added (i.e.,  $\alpha/3$ ) to obtain stricter interim stopping boundaries to enhance safety.

This optimization is performed assuming a vague Dirichlet prior Dir(0.05,0.1,0.15,0.7) for p. The prior is chosen such that it corresponds to a prior effective sample size of 1 patient, and the prior estimates of p\_eff and p\_tox match the values specified when the treatment is unacceptable. The above decision rule leads to the following optimal stopping boundaries:

Table 18: Optimized stopping boundaries

# patients treate	d Stop if # response <=	OR # toxicity >=
10	0	3
20	2	5
30	5	6

When the total number of patients reaches the maximum sample size of 30, we conclude that the treatment is acceptable if the number of responses are greater than 5, and the number of toxicities are less than 6; otherwise we conclude that the treatment is unacceptable. The go/no-go criteria in Table 18 are non-binding.

Below (**Table 19**) are the operating characteristics of the design based on 10000 simulations using the BOP2 web application (BOP2 V1.4.10.0), which is available at http://www.trialdesign.org.

Table 19: Operating characteristics

Scenario	Pr(Eff)	Pr(Tox)	Pr(Eff & Tox)	Early Stopping (%)	Claim Acceptable (%)	Average Sample Size
1	0.30	0.2	0.05	48.77	33.34	21.7
2	0.15	0.3	0.05	89.47	1.56	14.2
3	0.30	0.1	0.05	14.26	77.76	27.6
4	0.15	0.1	0.05	51.07	20.83	22.3
5	0.30	0.2	0.10	49.39	31.94	21.6
6	0.15	0.2	0.05	71.48	8.34	18.2
7	0.20	0.1	0.05	31.75	45.19	25.1
8	0.15	0.4	0.06	97.62	0.19	11.6
9	0.40	0.1	0.06	9.74	86.76	28.3
10	0.40	0.4	0.16	96.03	0.50	12.1

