Upon completion of the trial, efficacy (per ORR and toxicity rates will be summarized as proportions with corresponding 95% Agresti-Coull confidence intervals. Given 30 patients, the following table (**Table 20**) provides rates and confidence intervals over a range of incidences:

Table 20: Rates and Confidence Intervals

Incidence	Proportion (95% CI)
0/30	0 (0, 0.13)
1/30	0.03 (0, 0.18)
2/30	0.07 (0.01, 0.22)
3/30	0.1 (0.03, 0.26)
4/30	0.13 (0.05, 0.3)
5/30	0.17 (0.07, 0.34)
6/30	0.2 (0.09, 0.38)
7/30	0.23 (0.12, 0.41)

Protocol 2021-0547
Page | 51 04/25/2024

8/30       0.27 (0.14, 0.45)         9/30       0.3 (0.17, 0.48)         10/30       0.33 (0.19, 0.51)         11/30       0.37 (0.22, 0.55)         12/30       0.4 (0.25, 0.58)         13/30       0.43 (0.27, 0.61)         14/30       0.47 (0.3, 0.64)         15/30       0.5 (0.33, 0.67)         16/30       0.53 (0.36, 0.7)         17/30       0.57 (0.39, 0.73)         18/30       0.6 (0.42, 0.75)         19/30       0.63 (0.45, 0.78)         20/30       0.67 (0.49, 0.81)         21/30       0.7 (0.52, 0.83)         22/30       0.73 (0.55, 0.86)         23/30       0.77 (0.59, 0.88)         24/30       0.8 (0.62, 0.91)         25/30       0.87 (0.7, 0.95)         27/30       0.9 (0.74, 0.97)         28/30       0.93 (0.78, 0.99)         29/30       0.97 (0.82, 1)         30/30       1 (0.87, 1)		
10/30       0.33 (0.19, 0.51)         11/30       0.37 (0.22, 0.55)         12/30       0.4 (0.25, 0.58)         13/30       0.43 (0.27, 0.61)         14/30       0.47 (0.3, 0.64)         15/30       0.5 (0.33, 0.67)         16/30       0.53 (0.36, 0.7)         17/30       0.57 (0.39, 0.73)         18/30       0.6 (0.42, 0.75)         19/30       0.63 (0.45, 0.78)         20/30       0.67 (0.49, 0.81)         21/30       0.7 (0.52, 0.83)         22/30       0.73 (0.55, 0.86)         23/30       0.77 (0.59, 0.88)         24/30       0.8 (0.62, 0.91)         25/30       0.83 (0.66, 0.93)         26/30       0.87 (0.7, 0.95)         27/30       0.9 (0.74, 0.97)         28/30       0.93 (0.78, 0.99)         29/30       0.97 (0.82, 1)	8/30	0.27 (0.14, 0.45)

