25/30     0.83 (0.66, 0.93)       26/30     0.87 (0.7, 0.95)       27/30     0.9 (0.74, 0.97)       28/30     0.93 (0.78, 0.99)       29/30     0.97 (0.82, 1)	23/30	0.77 (0.59, 0.88)
26/30     0.87 (0.7, 0.95)       27/30     0.9 (0.74, 0.97)       28/30     0.93 (0.78, 0.99)       29/30     0.97 (0.82, 1)	24/30	0.8 (0.62, 0.91)
27/30     0.9 (0.74, 0.97)       28/30     0.93 (0.78, 0.99)       29/30     0.97 (0.82, 1)	25/30	0.83 (0.66, 0.93)
28/30 0.93 (0.78, 0.99) 29/30 0.97 (0.82, 1)	26/30	0.87 (0.7, 0.95)
29/30 0.97 (0.82, 1)	27/30	0.9 (0.74, 0.97)
	28/30	0.93 (0.78, 0.99)
30/30 1 (0.87, 1)	29/30	0.97 (0.82, 1)
	30/30	1 (0.87, 1)

In secondary analysis, ORR will be summarized separately by Notch status as proportions with corresponding 95% Agresti-Coull confidence intervals. The difference in ORR between Notch groups will be assessed by Fisher's exact test.

Other measures of response (CR, Cri, PR, relapse, radiographic tumor response, CNS remission, CNS relapse) and minimal residual disease (MRD) will be summarized as proportions with corresponding 95% Agresti-Coull confidence intervals.

Duration of Response (DoR), Overall Survival (OS), and event-free Survival (EFS) will be summarized using Kaplan-Meier methods.

In exploratory analyses, correlations between ORR and pharmacokinetic and pharmacodynamics markers will be summarized. Rates of patients transitioning to Hematopoietic stem cell transplant (HSCT) will be summarized. Endpoints may be further summarized separately by Notch status.

Additional statistical methods may be used.

The Investigator is responsible for completing an efficacy/safety summary reports and submitting it to the IND Office Medical Affairs and Safety Group, for review and approval.

This should be submitted after the first 10 evaluable patients complete 1 cycle of study treatment, and every 10 evaluable patients, thereafter. Efficacy summary will be submitted for every 10 evaluable patients after they complete 2 cycles of therapy.

Page | 52 04/25/2024

A copy of the safety summary report should be placed in the Investigator's Regulatory Binder under "sponsor correspondence".

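### The dose-based rule for response evaluability conflicts with the all-treated counts in Section 12 and, if applied to the primary ORR, can bias the reported rate and its confidence interval upward

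*Combined protocol and SAP*

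**What the plan says.** Section 9 (Response Definitions) sets two different evaluability rules. For response: "Patients will be considered evaluable for response if they have been administered greater than 50% of the dose of CB-103". For safety: "Patients will be evaluable for safety if they have been administered 1 dose of CB-103". The response rule does not say whether the dose is that of cycle 1 or of both cycles, or whether it is the planned or the modified dose.

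Section 12 counts patients in another way:
- Enrolment: "Up to 30 patients may be enrolled, without regard to Notch status".
- Table 18 gives its boundaries by number of patients treated (10, 20, 30).
- The final decision applies as follows: "When the total number of patients reaches the maximum sample size of 30". It requires more than 5 responses and fewer than 6 toxicities.
- Table 20, the interval table, is introduced with "Given 30 patients, the following table".
- Report timing, however, uses the Section 9 term: "Efficacy summary will be submitted for every 10 evaluable patients after they complete 2 cycles of therapy".

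Section 4.3 replaces patients removed during cycle 1, except those removed for toxicity or progression. Section 9.1.5 says that all patients are included, but only for event-free survival. No section names the analysis set for the primary ORR or says how a treated but non-evaluable patient is counted.

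**The concern.** Receiving more than half of the CB-103 dose is known only after treatment starts, and it depends on how the patient does. Patients who progress, die or have early toxicity are the likeliest to fall short of it. Those removed in cycle 1 for toxicity or progression are not replaced either, so under the Section 9 rule they could be neither replaced nor counted in the ORR.

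The missing period widens the problem. A two-cycle reading drops anyone who stops at the end of cycle 1, and a cycle 1 reading keeps them. The missing reference dose matters too. Section 5.1.3 allows some patients enrolled before Version 2.0 to stay on a lower CB-103 dose, and Section 6.1 allows dose reductions. Two analysts could therefore report different ORRs from the same data.

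At stake are the point estimate and 95% interval of the primary efficacy endpoint in a single-arm trial, where no comparator would show the selection.

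**Working it through.** **1. The plan's own figures.** Inputs from Section 12: λ = 0.57, α = 0.86, N = 30, prior Dir(0.05, 0.1, 0.15, 0.7). The marginal priors are Beta(0.15, 0.85) for efficacy and Beta(0.20, 0.80) for toxicity. The cutoffs are λ(n/N)^α for efficacy (0.222, 0.402, 0.570 at n = 10, 20, 30) and λ(n/N)^(α/3) for toxicity (0.416, 0.507, 0.570). The boundaries come out at ≤0/2/5 responses and ≥3/5/6 toxicities, exactly as in Table 18. Exact enumeration with looks at 10, 20 and 30 treated patients gives these probabilities of claiming acceptability:
- ORR 0.15, toxicity 0.20: 8.2% (Table 19: 8.34%).
- ORR 0.15, toxicity 0.10: 21.0% (Table 19: 20.83%).

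The design therefore works as stated on treated patients.

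**2. When the 50% threshold is passed.** Five days on and two off (Section 5.1.3) gives 20 dosing days per 28-day cycle and 40 over two cycles. With no missed or reduced doses:
- Cycle 1 reading: the threshold is first exceeded on the 11th dosing day, which is day 15.
- Two-cycle reading: it is first exceeded on the 21st dosing day, which is day 29. A patient who completes cycle 1 and stops has 20/40 = 50%, which is not more than 50%, and is non-evaluable.

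**3. Effect on one result.** Agresti-Coull: ñ = n + z², p̃ = (x + z²/2)/ñ, limits p̃ ± z√(p̃(1−p̃)/ñ), with z = 1.96 and z² = 3.84.
- 6/30: ñ = 33.84, p̃ = 0.234, half-width 0.143. Result 0.20 (0.09, 0.38), as in Table 20.
- 6/27 (three non-responders dropped): ñ = 30.84, p̃ = 0.257, half-width 0.154. Result 0.22 (0.10, 0.41).

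**4. Expected bias and coverage.** Assumptions, since the documents give no rate: a share f of the 30 treated patients is dropped, all of them non-responders, and the true all-treated ORR is 0.15. The apparent ORR is 0.15/(1−f). For coverage, responses X ~ Bin(30, 0.15), drops given X ~ Bin(30−X, f/0.85), and the interval is computed on X/(30 − drops). No early stop is applied, which the plan permits: "The go/no-go criteria in Table 18 are non-binding".

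| f | Apparent ORR | 95% CI coverage of 0.15 |
|---|---|---|
| 0 | 15.0% | 96.5% |
| 10% | 16.7% | 93.6% |
| 20% | 18.8% | 90.5% |
| 30% | 21.4% | 84.1% |

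**5. Direction.** If dropped patients respond at rate r, the apparent ORR is (0.15 − f·r)/(1−f). For f = 10, 20, 30%:
- r = 5%: 16.1, 17.5, 19.3%.
- r = 15%: no bias.
- r = 25%: 13.9, 12.5, 10.7%.

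Upward bias therefore requires that dropped patients respond less often than those kept.

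**The case against.** The strongest reply is that Section 12 already implies an all-treated denominator. Every count used for the decision or the interval refers to treated or total patients. The replacement rule in Section 4.3 fits counting toxicity and progression removals as failures, and the word evaluable appears in Section 12 only to time reports. This is a fair reading and may be what was intended. It stays an inference, because Section 9 states an explicit response rule and Section 12 uses its term for the efficacy summaries.

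The reply is also right that the drop rates are assumed and that the bias can vanish or reverse. Under the two-cycle reading, a day 28 responder who stops for transplant (Section 4.3.3) would be dropped, which pulls the ORR down.

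A reader might infer three stronger claims that the documents do not support:
- *The false-acceptance rate is inflated.* With looks on treated patients, the Section 9 rule does not touch Table 18, and the rate stays at 8.2% (toxicity 0.20) at every drop rate. It would rise to about 11–22% only if looks were filled to 10, 20 and 30 evaluable patients. That needs about 33 to 43 treated patients (30/0.9 to 30/0.7), above the cap of 30.
- *A lower confidence limit above 15% would be a false claim of efficacy.* Dropping two non-responders does move the lower limit from 0.140 (8/30) to 0.151 (8/28). But the plan decides on response and toxicity counts and uses the interval only as a summary.
- *Different sets for response and safety contradict the joint model.* Section 12 defines paired outcomes "indicating that patients experience efficacy and toxicity, respectively", but it also allows the two endpoints to be monitored separately through their marginal distributions.

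**Conclusion.** The point holds in conditional form and should be fixed. Section 9 contains a response rule based on treatment received, with no period or reference dose. It conflicts with the counts in Table 18, the final rule and Table 20, and no text says which governs the primary ORR. If it is applied, the reported ORR and interval are biased upward whenever dropped patients respond less often than those kept. That is plausible for early progression, death or toxicity, but not certain.

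The effect is modest for a few exclusions, as the 6/30 and 6/27 comparison shows. At an assumed 30% of dropped non-responders it is material: 6.4 points on a true ORR of 15%, with coverage of 84.1%. These sizes rest on assumed drop rates, on every dropped patient being a non-responder, and, for coverage, on no early stop. The defect concerns the reported estimate and interval, not the go/no-go on treated patients.

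**What to change.** In Sections 9 and 12:
- Define the primary ORR, its confidence interval and every Table 18 efficacy look on all patients who received at least one dose of CB-103. Section 9 already uses this set for safety.
- Count as a non-responder anyone without a documented CR, CRi or PR by the end-of-cycle-2 response assessment. That assessment should include its visit window and the repeat marrow that Section 4.3.2 requires between days 66 and 70 when the day 56 marrow is hypocellular. It should also allow for a cycle 2 start delayed under Section 4.3.1. A plain cutoff at the end of cycle 2 would turn a remission documented at that repeat marrow into a failure.
- Use the same set in the efficacy-summary sentence that closes Section 12.
- State the period and the reference dose for the 50% threshold, and report the evaluable-set ORR as a sensitivity analysis only.

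In Section 4.3, state whether replaced patients who had been dosed stay in the denominator, and reconcile this with the cap of 30.

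The cost is wording. No new data are needed, and no new boundaries if n stays at 30. The downside is a slightly less favourable reported ORR, because dropouts unrelated to the drug count as failures.
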